Sample size in each group¹-range of options for Phase II trial (our proposed sample sizes for each outcome are in **bold**).

1. We used the NQUERY multiple group sample size programme for three groups and assumed both clinical score and control groups had similar figures; if the control group fares worse than the clinical score group (i.e. the spread of observations is wider) fewer numbers will be needed in each group. The numbers in each cell are the numbers with complete data required in each group.

Statistics analysis, type and frequency

We will perform analysis of covariance for the main continuous outcomes (diary scores, symptom duration). Log rank tests and Cox regression will be used to assess the time to return to the surgery with a new episode of sore throat as we used in our previous trial¹⁹ (which will involve 'censored' data due to variable follow-up time available). Logistic regression will be used for dichotomised outcomes (e.g. belief in the need to see the doctor, belief in antibiotics) and Poisson regression for incidence rates (e.g. rates of return to the surgery with sore throat - which more closely follow a Poisson distribution rather than a normal distribution). The models will control for confounders if appropriate (although randomisation should ensure that confounders are balanced between groups). We will present the results with 95% confidence intervals. The primary analysis will be an intention to treat analysis based on finding the differences proposed. We will specify *a priori* key subgroups as potential effect modifiers based on an updated literature review prior to analysis (currently we specify baseline symptom severity, and GPs' view of whether the infection is viral or bacterial). We will also perform secondary analyses: a) a per protocol analysis, and also b) an equivalence analysis if appropriate (having established in our qualitative work what patients regard as equivalent). The clinical and demographic characteristics of a) eligible patients not consenting, and also b) those not followed up, will be compared to assess respectively possible selection and non response bias.

Our key presentation of the data will be of the main symptomatic outcomes alongside the data on antibiotic use and side effects from antibiotics

Economic analysis.

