The Social Judgment Theory advocates a 'representative design' ⁴³, therefore vignettes should be representative of patients that doctors deal with in their practice. To this effect, cue profiles will be constructed from the patients participating in phase 1. Out of these, a certain number of cue profiles will be randomly selected. The number will depend on the number of cues that we decide to include – as a rule-of-thumb, 5-6 cues require a minimum of 30 cue profiles, but feasibility (stamina and patience of GPs) argues for a limited number of cues and cue profiles. Vignettes will be presented to GPs who will be asked to estimate the likelihood of each patient having streptococcus (on a 0-100 VAS), and to decide whether they would prescribe antibiotics or not. The judgment and treatment policies of each GP will then be modelled as separate regression equations. These equations will show which cues each GP actually used in assessing likelihood of infection and making treatment decisions (a cue is considered used if its regression co-efficient is significant). We hypothesise that GPs who took part in the main trial are more likely to use the RADT results or the clinical scores than 'naïve' GPs both to assess likelihood of streptococcus infection and to decide about treatment⁴⁴. To assess consistency of cue use and judgments/decisions, the same vignettes will be presented to the GPs a week later in a different order. Development and preparation of the vignettes will commence during the last 9 months of the study, but the final version of the vignettes can only be sent to the GPs once we have the results of the trial. We will therefore analyse the JA study in the penultimate month of the proposed study period allowing a month for write up.

Risk and benefits for trial participants

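### Judging cue use by significance in each GP's own regression can, for the prescribing decision with a logistic Wald test, class the closest RADT followers as non-users and reverse the contrast between trial and naïve GPs

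*Protocol*

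**What the plan says.** The Protocol section on assessing the potential effect on clinical behaviour describes a vignette study at the end of phase II. For each vignette the GP is asked to "estimate the likelihood of each patient having streptococcus (on a 0-100 VAS), and to decide whether they would prescribe antibiotics or not". The analysis is by individual GP: "The judgment and treatment policies of each GP will then be modelled as separate regression equations". Cue use is then defined by a test: "a cue is considered used if its regression co-efficient is significant". That definition serves a stated hypothesis, that "GPs who took part in the main trial are more likely to use the RADT results or the clinical scores than 'naïve' GPs", both for the likelihood of infection and for treatment.

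On size, the section gives a rule of thumb: "5-6 cues require a minimum of 30 cue profiles, but feasibility (stamina and patience of GPs) argues for a limited number". The vignettes are shown twice: "To assess consistency of cue use and judgments/decisions, the same vignettes will be presented to the GPs a week later in a different order".

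The section names no regression type, test or significance level. The phase II section on statistical analysis says "Logistic regression will be used for dichotomised outcomes", but does not extend this to the vignette study.

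**The concern.** A significance rule assumes that the stronger a GP's use of a cue, the more likely the coefficient is to be significant. For a yes/no decision modelled by logistic regression and tested by Wald, this is true only up to a point. When decisions line up almost perfectly with the RADT result, no finite maximum likelihood estimate exists, the standard error grows faster than the coefficient, and the p-value moves towards 1. The rule then records that the GP did not use the RADT.

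Close adherence is plausible among trial GPs. In the RADT arm described under planned interventions, antibiotics are offered only after a positive result, and GPs are shown the trial findings before they see the vignettes. If trial GPs adhere more closely than naïve GPs, the rule can report fewer RADT users among them, which is the opposite of the hypothesis.

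**Working it through.** **Plan's own figure.** Thirty profiles for 5-6 cues is 30/6 = 5 to 30/5 = 6 profiles per cue. No power, effect size or alpha is attached, so there is nothing to reproduce.

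**Inputs from the Protocol.** 30 vignettes, 5-6 cues, a binary decision and a 0-100 rating; 25% with streptococcus (phase 1 sample size), used as one value for the share of RADT-positive vignettes.

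**Assumptions.** Two-sided alpha 0.05; other RADT-positive shares (30% and 40% among them); adherence p means that each decision follows the RADT result with probability p, independently, with no effect of the other cues.

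**Step 1: why the Wald test fails.** With the RADT as the only cue, cross-classify result by decision, with cells a, b (positive: prescribed, not prescribed) and c, d (negative: prescribed, not prescribed). The log odds ratio is ln(ad/bc), with standard error √(1/a + 1/b + 1/c + 1/d). If b or c is 0, both are infinite. Adding cues to the model cannot make the RADT coefficient finite again. An example six-cue-scale fit for a GP who follows the RADT exactly gave p = 0.999 for the RADT.

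A GP with at most one departure from the RADT always has an empty cell. The probability of that is p^30 + 30(1 − p)p^29:
- p = 0.80: 0.0012 + 0.0093 = 0.011
- p = 0.90: 0.042 + 0.141 = 0.18
- p = 0.95: 0.215 + 0.339 = 0.55
- p = 1.00: 1

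These are lower bounds. Several departures in the same direction also leave an empty cell, and the other cues add further separation.

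**Step 2: share of GPs classed as RADT users, 30 vignettes and 6 cues (simulation).**

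| Adherence | Logistic, Wald | Logistic, likelihood-ratio | Linear on 0/1 |
|---|---|---|---|
| 80% | 35-54% | 87% | 83% |
| 90% | 15-21% | 97% | 99% |
| 95% | 4% | 98% | 100% |
| 100% | 0% | 100% | 100% |

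The last two columns come from a run with the RADT positive in 30% of vignettes; its Wald figures were 46%, 21%, 5% and 0%. A further run with 25-50% positive gave 39-55%, 16-24%, 4-7% and 0% for Wald.

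**Step 3: other cues active.** With 5 or 6 cues, the other cues at log-odds 0.5 (assumed) and the RADT positive in 25% or 40%, Wald flags 9-17% of GPs at RADT log-odds 1, 22-43% at 2, 27-51% at 3, 18-29% at 4, 3-5% at 6 and under 1% at 8. Detection rises and then collapses. The likelihood-ratio test gives 83-93% at log-odds 3 and 98-100% at 6, but also 9-13% false use at log-odds 0.

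**Step 4: more responses.** If the repeat presentation were pooled (60 responses, treated as independent), Wald gives 87-96% at log-odds 3 and 14-23% at 6, and still 0% for exact followers. In the adherence model it gives 95% at 80% adherence and 65% at 90%. The collapse moves but does not disappear.

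**Step 5: likelihood rating.** Ordinary linear regression on 30 vignettes, residual SD 15 points (assumed): a RADT effect of 10 points is flagged in 25-33% of GPs, 20 points in 72-86%, 30 points in 96-99%, and 50 or more in 100%. This rises steadily, so there is no reversal.

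**Step 6: an illustrative contrast.** With 20 naïve GPs at 80% adherence and 20 trial GPs at 95% (all assumed), 150 replicates gave on average 10.3 naïve and 1.0 trial GPs flagged by the Wald rule. A GEE across GPs with a group by RADT interaction was significant in the correct direction in all 150.

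**The case against.** The strongest reply is that the Protocol never commits to a Wald test, nor to logistic regression for this sub-study. Under likelihood-ratio or linear tests, close followers are classed as users and the contrast keeps its direction. The choice of test is a detail that an analysis plan may settle. This stands, and it makes the finding conditional. It does not dispose of it: the Protocol itself fixes the per-GP rule, a rule about whether a coefficient is significant points to that coefficient's own test, and nothing in the text guards against separation. Changing the test alone is also only a partial cure. In one run the likelihood-ratio test flagged 84-92% at 80% adherence and 97-99% at 95%, so a real difference is squeezed against the ceiling.

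Second, the 80% against 95% contrast and the group sizes are not in the documents. Trial GPs use three strategies, and RADT use is provisionally targeted to intermediate scores. If naïve GPs are weak users, Wald can order the groups correctly: 50% adherence gives 5% flagged, 70% gives 34% and 80% gives 46%. This stands; reversal is possible, not certain.

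Third, 30 is a minimum. True, but feasibility is said to argue for few profiles, and more vignettes do not cure exact separation.

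Fourth, fitting each GP separately is the purpose of a judgement analysis. This stands for description, and the per-GP equations can remain. It does not justify testing a group hypothesis through per-GP p-values.

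A reader might infer that the whole sub-study reverses, or that research objective 5 is answered wrongly. The documents do not support this. The likelihood rating is half of the hypothesis and is unaffected, objective 5 is exploratory, and the section does not say that the groups will be compared by counting flagged GPs.

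**Conclusion.** The concern holds for the treatment-decision regressions, on condition that cue use is judged by a logistic Wald test. Then about 35-54% of GPs are classed as RADT users at 80% adherence, 15-21% at 90%, 4% at 95% and 0% at 100%, and the contrast between trial and naïve GPs can reverse. The failure for exact followers is a mathematical property of the test. The intermediate figures rest on the assumed alpha, independent departures and cues without effect, though the same rise and fall appears when the other cues are active. For the likelihood rating, the only weakness is low power for weak cue use. The point merits a change because a stated rule can give the wrong answer to the sub-study's own hypothesis. It concerns a secondary sub-study and leaves the primary trial result untouched.

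**What to change.** Test the stated hypothesis in one model across GPs, with responses clustered by GP and a GP-group by RADT (or score) interaction: a mixed logistic or GEE model for prescribing and a linear mixed model for the likelihood rating. Keep the per-GP equations as description, but report cue use as the size of a penalised or shrunken weight. If a yes/no label is kept, base it on a penalised or likelihood-ratio test, not on a Wald p-value.

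The change uses the same GPs and vignettes. It costs slightly more analysis work, and individual labels become estimates instead of a yes or no.
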